The PI will collect all baseline data before the participant is randomized to the intervention or sham/wait list control group. In order to ensure rigor, patients and PI are blinded to study assignment. The intervention/sham will be set-up by the RA and will be collected after the PI leaves the department so those collecting data will not know which group the participant has been/will be participating in. The RA who is trained in both NMES and Sham intervention will then look at the randomization schedule, and set up and train the participants on equipment use after the data has been collected.²⁷ Once trained, participants will be contacted via phone weekly by the RA who initially trained them (in order to maintain blinding) to determine if participants are following protocol and placement as taught, if the participant is tolerating the intervention, skin condition under the electrodes, and if there are any questions or problems with the machine. The RA applying the intervention will not have any part in the data collection of the rest of the measurements (other than adherence, tolerance and problems with equipment).

The Empi Continuum electrotherapy system made by Empi, Inc. (Clear Lake, South Dakota) is chosen for NMES in this study because it is already available to the PI, it has both the intervention and sham settings, and is able to track adherence (total number of sessions, total session time, average session time, average intensity). Each machine will be calibrated before use for each participant and also checked with each return visit. The output of the stimulator will be checked with an oscilloscope to ensure consistency between the current reading on the stimulator and the actual current output every time the participant returns. NMES will be set up with the machine on simultaneous large muscle atrophy setting with 500 ohm with peak of 50 volts, the “self-adhesive electrodes positioned on the thighs approximately 5 cm below the inguinal fold and 3 cm above the upper patella border” as described by Gobbo.²⁸ When applying the stimulation, the intensity will be gradually increased from an intermittent tingling until a

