gentle pumping sensation is felt. Participants will direct the amount of stimulation acceptable on both thighs to improve acceptance of the modality.^{10,24,29-31} To assist better tolerance large electrodes (2x4) will be used and participants will also be instructed to be in a seated position with chair close to the wall so that their leg is 90-degree angle and then push against the wall to decrease any uncomfortable feeling during the contraction. For the Sham group, electrodes will follow the same landmarks, but the stimulation will only increase to an intermittent tingling sensation with the machine setting on TENS instead of NMES which is not enough to make noticeable changes in muscle mass or circulation.³² Participants in both groups will be given written instructions and contact information of the person (RA) to contact should there be any problems or concerns with the intervention. All participants will do a return demonstration to assure proper knowledge has been gained. Adherence to the study protocol will be determined by the amount of time the EMPI machine records that it was used, the intensities utilized along with verbal verification during the weekly phone calls.

NMES Protocol Summary

- 5 sessions per week for 6 weeks done independently at home, with 15 minutes per session (15 stimulations per day/session, 15 seconds stimulation on, 15 seconds recovery time) to both legs.
- Intervention group only: We expect the participant to develop tolerance to the treatment and thus increase the intensity of the NMES over time.
- At the end of the trial, the participants will return to have all measures repeated. Sham group will then be offered the active treatment. In previous HF studies (non-NMES) done by the mentor of this grant, no participants have accepted the offer of the intervention after completion of the sham/control so this number is expected to be very small.
- Participants will be encouraged to begin a formalized exercise plan such as Silver Sneakers, a home based cardiac rehabilitation or institutional cardiac rehabilitation program.
- Finally, 3 months after the intervention/sham was completed participants will return one final time to have all measures repeated to allow for evaluation of activity levels following completion of the intervention.

Retention

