Participants will be told prior to enrolling in the study that they could be randomized to the sham treatment group, and if so, they will be given the opportunity to participate in the NMES protocol after completing the sham intervention. Individualized calendars will be provided to participants to assist in reminding them when which assessment is scheduled. Participants in both groups will be provided the same compensation of \$50 for each visit where physical data are collected, \$10 for each weekly phone call (\$60) with RA to assess adherence/problems. Total money paid to participants completing all components of participation will be \$210.

- Payment 1: \$50 for baseline measures (paid upon return of ActivPal, paid via voucher checks sent in the mail)
- Payment 2-6: \$10 for phone call/verification (paid weekly following the phone call via voucher checks sent in the mail)

- Payment 5: \$50 for post intervention measures (paid upon return of ActivPal, after the second physical testing visit-mailed to participant)
- Payment 6: \$50 for Final post intervention measures (paid upon return of ActivPal after the third physical testing visit-mailed to participant)

If participants fail to return the equipment they will not receive the payment scheduled for that visit.

Instruments and Measures

1. Dual-energy x-ray absorptiometry (DXA) will be used to determine if there is a measurable change in fat mass and skeletal muscle mass as a result of NMES intervention (**specific aim 1**). Other studies have found an increase in muscle strength but muscle mass was not measured with DXA. DXA is chosen because it is quick (10-15 minutes), relatively cheap (compared to CT), analysis is straight forward and patients are more accepting of DXA procedures than CT.³³ Hologic Discovery-W densitometer is the DXA machine we will be using with Apex software version 2.3. Calibration will be conducted every day a participant is scheduled to come in and weekly scanning of manufacturer supplied supine phantom will also be ran to determine that no instrumentation drift has occurred. Coefficients of variance were reported to be between 1-3% thus showing this machine to have an excellent precision.³³ DXA is the gold standard in the measurement of body composition.³⁴ Total and segmental (bilateral upper leg) body composition will be assessed according to the differential degree of photon attenuation at two levels of energy as described by Steiner.³⁵

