21. If the participant reports the feeling is still uncomfortable or “bit” lower the WIDTH by 8 and see if that makes it better. (Can adjust in increments of ±4 to get the “best” feel for participants. Be sure to record the final setting you programmed into the machine in Redcap and on your participant call sheet.) To make adjustments to Width, You (not the participant!) need to press the home button, NMES, Custom, the press the left lower button until you see “Width”, then use the right lower button to make the adjustment, then press OK and have the participant try again.

Once you are confident the participant settings are comfortable for the patient and only intensity needs to be adjusted, LOCK the device so the participant cannot change the settings themselves.

1. Press the Home button, config (right lower), locks (right lower)
2. Notice the NMES L. Muscles and press the right top button, which locks that option
3. Press the left lower button to bring up S. Muscles and press the right top button twice to get a circle with a line through it. Now that option will no longer show for participants. Repeat for TENS and Edema then press home and note only L. Muscles is an option besides config.

Standard operating procedure when EMPI units are returned

Expect participants to bring the unit in the study canvas bag along with any unused sealed supplies.

Step 1: log into RedCap, bring up the data entry for the EMPI machine, enter the study ID.

Step 2: once you have the Canvas bag with EMPI unit, use the wipes designated for cleaning the machine to wipe down the outside of the machine and the lead wires and allow them to air dry.

Step 3: turn on the machine, identify if NMES or TENS showing on the main menu and enter that data into RedCap

Step 4: press the home button, config button (right lower), data button (left upper).

Step 5: enter the number of sessions into RedCap, press the left down button

Step 6: enter the Total hours into RedCap, press the left down button

Step 7: enter the average time into RedCap, press the left down button

Step 8: enter the CH 1 intensity into RedCap, press the left down button

Step 9: enter the CH 2 intensity into RedCap, press the home button. Double check you have entered all data into RedCap.

Step 10: press the home button, config, clear (right lower), data, and then home. The data has been erased from the machine and is ready for the next participants set up.

BISTRO Patient Instructions:

Empi Unit

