4. Plug the wire connector from the patch to the wire on the machine. Note: The wire connectors may connect to either the red or black connectors. The black wire connected to the patch at the top of the thigh and the red connector the patch near the knee. If there is wire damage call research assistant for a new set.
5. Place the patches in the correct locations as indicated in the diagram on page 2. Stick the center of the patch on the desired area of the skin, and then flatten the sides of the patches onto the skin.

6. Remove the unit from the canvas bag and turn the unit on using the ON/OFF button in the middle of the bottom row on the unit, just below the screen. When you turn on the unit, the screen will present the Empi logo (See picture above).
7. Next, the screen should display an “In-Progress” message indicating that the unit is ready for use.
 - a. If the screen goes to a menu that displays options for you to select (i.e., NMES, TENS, EDMEA, CONFIG), call the research assistant as additional directions will be needed for you to safely use the machine.
8. Once the “In-Progress” screen appears, you need to increase the level of intensity for treatment. Adjust the intensity to the level specified by the research assistant.
 - a. To increase the intensity for Channel 1, press the top button on the left-hand side of the screen. To decrease the intensity for Channel 1, press the bottom button on the left-hand side of the screen.
 - b. To increase the intensity for Channel 2, press the top button on the right-hand side of the screen. To decrease the intensity for Channel 2, press the bottom button on the right-hand side of the screen.

- c. Note: Once the intensity is set and left alone for 20 seconds, the unit will lock the buttons to prevent an unwanted change. In order to change the intensity after the unit is locked, press the decrease intensity button on the desired channel to unlock the unit so you can change the intensity.
- d. Unit will stop running after 15 minutes. You can now turn off the machine by pressing of on/off button for 2 sections and remove the patches.

9. Removing the patches

- a. Turn off the unit before removing the patches.
- b. Carefully pull the patch off the skin starting at a corner. The wire connectors should **not** be used to help pull the patches off! Pressing on the skin with your other hand close to where you are removing the patch makes removal easier.

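### Participant blinding is not protected at the device: the stimulator's menu can name the allocated mode, and the SOPs and handout disagree about what a participant's screen shows

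*Combined protocol and SAP*

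**What the plan says.** Section 5 (Intervention and Sham/Wait List Control Conditions) makes the claim: "In order to ensure rigor, patients and PI are blinded to study assignment". Both arms use the same Empi unit, and the sham arm has "the machine setting on TENS instead of NMES". Treatment is "5 sessions per week for 6 weeks done independently at home".

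Section 5 (Retention) has the possibility of a sham allocation disclosed before enrolment. About people who turn out to be in that arm it adds: "they will be given the opportunity to participate in the NMES protocol after completing the sham intervention".

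Section 12B bears on the display in three places:

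- **Returned units, step 3.** Staff "turn on the machine, identify if NMES or TENS showing on the main menu and enter that data into RedCap".
- **Patient instructions, Using Your Empi Unit, steps 7 and 7a.** After power-on the participant should see an In-Progress "message indicating that the unit is ready for use". The exception is then covered: "If the screen goes to a menu that displays options for you to select (i.e., NMES, TENS, EDMEA, CONFIG), call the research assistant".
- **Lock steps at the end of the TENS and NMES set-up procedures.** These are meant to stop participants changing settings. The text is the same in both procedures: lock the large-muscle NMES option, hide the small-muscle, TENS and edema options, then press Home and confirm that only large muscles and the configuration option remain.

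**The concern.** The mode is the allocation, so a participant who reads the mode name, and who has been told that NMES is what the sham group gets afterwards, can work out the arm. The unit is at home, unsupervised, for 5 × 6 = 30 scheduled sessions. The lock is described as a guard against changed settings, not as masking. The documents give participants no neutral mode names, no instruction to keep away from the menu, and no question at the end about which arm they thought they were in.

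Most outcomes are open to expectation. MLHFQ, MSAS-HF, PROMIS fatigue, BPI and PHQ-8 are self-reported; the 6MWT, dynamometer, sit-to-stand and TUG depend on effort. Together these make up Aim 3 and much of Aims 1 and 2. A difference produced by knowing the arm would be reported as double-blind evidence, and nothing collected would let a reader judge whether the blind held.

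**Working it through.** The plan gives no figure on this point to reproduce. The check sets the texts side by side and then adds one illustration with assumed inputs.

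**1. Can the mode be read from the unit?** Return step 3 relies on it: staff power the unit on and read the mode. Step 4 then presses Home to reach the configuration menu, again with no unlocking. The lock steps themselves end by pressing Home to view the menu. So the menu of a locked unit can be reached by staff without a code. Nothing says a participant could not do the same, and nothing says that any does.

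**2. What does a participant see at power-on?** The handout (step 7) says the In-Progress screen. The return procedure (step 3) goes from power-on straight to the main menu. These do not agree. Step 7a accepts that the menu may appear at home, and by the time the participant calls, it has been seen. The documents do not say whether the In-Progress screen names the mode.

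**3. What would a sham unit's menu show?**

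| Text in Section 12B | Sham unit should show |
|---|---|
| TENS set-up, steps 3 to 9 | a TENS programme, selected and configured |
| TENS set-up, lock steps, taken literally | large muscles (NMES) only; TENS hidden |
| Returned units, step 3 | TENS |

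The second row conflicts with the other two. Taken literally, it would give both arms the same menu, and return step 3 could never record TENS. It looks like text carried over from the NMES procedure, but the documents do not settle it.

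**4. Would the name mean anything to the participant?** Retention links NMES with the treatment that sham participants have not had. Handout step 7a puts NMES and TENS before the participant as different options.

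**5. Illustration of size (assumed inputs).** Take 27 completers per arm (Section 8, Power Considerations), no true effect, and a two-sided 0.05 two-sample test of change. Assume a correlation of 0.5 between time points, so SD of change = SD × √(2(1 − 0.5)) = SD. An expectation difference of d SD averaged over the arm gives a noncentral t with df = 2 × 27 − 2 = 52 and noncentrality d × √(27/2) = 3.674d.

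| Whole-arm d (assumed) | Noncentrality | Rejection rate |
|---|---|---|
| 0 | 0 | 5% |
| 0.1 | 0.37 | 6.5% |
| 0.2 | 0.73 | 11.1% |
| 0.3 | 1.10 | 19.1% |
| 0.4 | 1.47 | 30.3% |

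If only some participants reach the menu, the effect is diluted. A 0.4 SD effect in half of them averages 0.4 × 0.5 = 0.2 SD (11.1%); in a quarter, 0.4 × 0.25 = 0.1 SD (6.5%). This test is also simpler than the planned three-time-point repeated-measures model. The table shows how the result depends on d; it does not estimate d.

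**The case against.** The strongest reply is that intended use never shows the menu. The In-Progress screen should appear at start-up, participants are trained on the on/off and intensity buttons, the unit is locked, and return step 3 is a staff task after treatment has ended. This stands as a limit: a reader might infer that blinding will fail, or has failed, and the documents do not support that. It does not remove the risk, because the handout itself provides for the menu appearing at home.

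Second, a reader might say that nothing hides the mode, or that a sham participant would see TENS. Neither can be asserted. The lock steps do hide options, and the TENS version read literally hides TENS. What stands is the contradiction between the lock steps, return step 3 and the handout.

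Third, that participants identify NMES as the active treatment is an inference from the protocol's account of what they are told. The consent pages are not in the review copy. The inference is reasonable, but it is not established. Excluding earlier NMES or TENS users (Section 3) limits recognition by feel, not by reading a name.

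Fourth, sensation is a more direct route to unblinding: active stimulation must make the muscle contract and sham must not. This is true and separate. Masking a label would not remove it, and it means that an allocation guess cannot be attributed to the label alone. It is a further reason to record the guess and the reason for it.

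**Conclusion.** The point holds as a gap in protection. Blinding is claimed, the mode is the allocation, the unit can display the mode, participant materials print both names, and no blinding check is described. Blinding can therefore fail for participants who reach the menu. How many would do so is unknown, and until the three parts of Section 12B are reconciled, so is what they would see.

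The size of any bias is unknown. A reader might carry away a 30% false-positive rate, but that needs an assumed 0.4 SD expectation effect across a whole arm; at 0.1 SD the rate is 6.5%. Nor does the concern extend to every Aim 1 outcome: DXA thigh lean and fat mass is neither self-reported nor effort-dependent and is not materially exposed. The conclusion rests on the Retention text reflecting what participants are actually told, and on the menu being reachable without a code, as the return procedure implies.

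**What to change.** 1. **Wording.** In handout step 7a, replace the parenthesis that names the modes with a neutral phrase such as a list of options. Use neutral programme names in all participant materials and conversations.
2. **Display.** Reconcile the lock steps in the TENS set-up procedure with return step 3 and handout step 7, so that any screen a participant can reach does not distinguish the arms. Mask the mode label only if intensity and error messages stay readable; whether a physical mask can do this is unproven. Tell participants to use only the on/off and intensity buttons.
3. **Check.** At the post-intervention visit, before the sham group is offered active treatment, record the participant's and the PI's guess of allocation and the reason for it. Report this descriptively when interpreting self-reported and effort-dependent outcomes, and note that guesses may also reflect felt contraction or perceived benefit. For that reason, do not attach an automatic rule to the result.

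The cost is minor handout and SOP edits and one extra question at one visit. The analysis model and sample size are unaffected.
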